#### 4.6. Other Analyses

Not applicable.

## 4.7. Interim Analyses

No interim analysis is planned.

Final analysis will be conducted once anti-RV IgA ELISA testing at Visit 3 (1 month after Dose 2) is completed and all the immunogenicity data are available. This final analysis will include immunogenicity and safety data up to Visit 3 and a CSR will be written.

An EoS analysis with all data including the data obtained during ESFU period will be performed. An integrated CSR will be written and made available to the investigators and submitted to regulatory authorities as appropriate.

*Note: If there is a delay in availability of the immunogenicity data, leading to a window between the 2 analyses shorter than what is planned at the time of protocol writing, only 1 statistical analysis including all immunogenicity and safety data will be performed and 1 study report will be developed.*

## 4.8. Changes to Protocol Defined Analyses

There were no changes or deviations to the originally planned statistical analysis specified in the protocol (Dated: 13 May 2022).

# 5. SAMPLE SIZE DETERMINATION

A maximum of 2000 participants (1000 per arm) will be randomized such that approximately 1500 evaluable participants complete the study, considering that 25% of the participants will not be evaluable for the analysis of the primary endpoint leading to 750 evaluable participants per arm.

To control the type 1 error for the primary objectives and first secondary objective a hierarchical procedure will be used. Namely the primary objective on ratio of anti-RV IgA Ab GMCs will be conclusive if the success criterion is reached and the first primary objective is met. The first secondary objective will be conclusive if the success criterion is reached and the 2 primary objectives are met.

The sample size provides at least 90% power to reach the first primary endpoint (see [Table 3](#)) and at 80.7% power to reach the second primary endpoint. 80.7% is a very conservative power estimate and is obtained as 100% minus the sum of type II errors for the 2 primary objectives, see [Table 3](#) and [Table 4](#). Using the same approach, the power to meet the first secondary objectives will be at least 67% power.

### 5.1.1. Power for non-inferiority in seroconversion

The power presented in [Table 3](#) is based on PASS 2019 (one-sided Non-Inferiority Tests for the Difference Between Two Proportions), under the alternative of a 70% and 67.8%

seroconversion rate for *Rotarix* and *Rotarix* PCV-free, respectively, [Miettinen](#) and [Nurminen](#)'s Likelihood Score Test of the Difference).

**Table 3 Probability that the lower limit of the 95% CI around group difference in seroconversion rate (*Rotarix* PCV-free minus *Rotarix*), 1 month after Dose 2 of *Rotarix*, is  $\geq -10\%$**

Expected Seroconversion rate ( Rotarix / Rotarix PCV-free)	N evaluable (each Rotarix group)	Power	Alpha
70%* / 67.8%	750	90%	0.025

\* = Reference from Rota-075

N = number of participants

### 5.1.2. Power for non-inferiority in GMC

The power presented in [Table 4](#) is based on PASS 2019 (one-sided non-inferiority test for 2 independent means, under the alternative of equal variance & alpha=2.5%).

**Table 4 Probability that the lower limit of the 95% CI around the anti-RV IgA Ab GMC ratio (*Rotarix* PCV-free / *Rotarix*), 1 month after Dose 2 of *Rotarix*, is  $\geq 0.67$**

Endpoint	True group GMC ratio	Standard deviation [ $\text{Log}_{10}$ (titer)]	N evaluable (each Rotarix group)	Power	Alpha
Anti-RV IgA Ab concentration	1	0.797*	750	99.0%	0.025
Anti-RV IgA Ab concentration	0.91	0.797*	750	90.7%	0.025

\* = Reference from Rota-075

N = number of participants

### 5.1.3. Power for non-inferiority in the percentage of participants with serum anti-RV IgA antibody concentrations greater or equal to 90 U/mL 1 month post Dose 2

The power presented in [Table 5](#) is based on PASS 2019 (one-sided Non-Inferiority Tests for the Difference Between Two Proportions), under the alternative hypothesis of a 45.7% and 43.5% percentage for *Rotarix* and *Rotarix* PCV-free, respectively, [Miettinen](#) and [Nurminen](#)'s Likelihood Score Test of the Difference).

**Table 5 Probability that the lower limit of the 95% CI around group difference in the percentage of participants with serum anti-RV IgA antibody concentrations greater or equal to 90 U/mL (*Rotarix* PCV-free minus *Rotarix*), 1 month after Dose 2 of *Rotarix*, is  $\geq -10\%$**

Expected rate ( Rotarix / Rotarix PCV-free)	N evaluable (each Rotarix group)	Power	Alpha
45.7%* / 43.5%	750	86.2%	0.025

\* = Reference from Rota-075

N = number of participants

## 6. SUPPORTING DOCUMENTATION

### 6.1. Appendix 1 Study Population Analyses

As per EudraCT reporting requirement, a summary of number of participants enrolled by country and by age category will be provided for the enrolled set.

#### 6.1.1. Participant Disposition

Number of enrolled participants and reason for exclusion from ES will be described by group.

Number of vaccinated participants and reason for withdrawal from the study will be described by group for the ES.

The distribution of participants enrolled in each site will be tabulated across and per study group for the ES.

Number of ES participants excluded from PPS analyses will be tabulated for each group based on the reason for exclusion.

#### 6.1.2. Demographic and Baseline Characteristics

The demography and baseline characteristic summaries will be provided for both ES and PPS.

The median, mean, range and standard deviation of age (in weeks) for each dose of *Rotarix* and for gestational age (in weeks) will be computed by group. Median, mean and standard deviation of height in centimeter and weight in kilogram at Visit 1 will be computed by group. The study sites, geographical ancestry and sex composition will be presented by group.

#### 6.1.3. Protocol Deviations

Important protocol deviations will be summarized.

Protocol deviations will be tracked by the study team throughout the conduct of the study. These protocol deviations will be reviewed to identify those considered as important as follows:

- Data will be reviewed prior to freezing the database to ensure all important deviations (where possible without knowing the study intervention details) are captured and categorised in the protocol deviations dataset.
- This dataset will be the basis for the summaries of important protocol deviations.

Protocol deviations which result in exclusion from the analysis set will also be summarized.

- Data will be reviewed prior to [unblinding and] freezing the database to ensure all deviations leading to analysis population exclusions are captured and categorised in the protocol deviations ADaM dataset (note these exclusions are not captured in the SDTM dataset).

The following deviations will be considered important protocol deviations.

Codes 800, 900 and 1030 will lead to elimination from the ES and the PPS. The other codes are specific to the PPS. Refer to Section 3 for the summary of protocol deviation leading to elimination from analysis set.

Code	Decode: Condition under which the code is used
800	Fraudulent data
900	Invalid informed consent
1030	Study vaccine dose not administered but participant number allocated: participants enrolled but not vaccinated
1050	Randomization failure: forced or manual randomization*. First dose of vaccine administration not aligned with the randomized treatment.
1040	Administration of concomitant vaccine(s) forbidden in the protocol: Administration of a non study HRV vaccine or non routine vaccine starting from 30 days before the first vaccination up to Visit 3 blood sample.
1060	Randomization code broken at the investigator site: Participants unblinded in the central randomization system or unblinding reported as protocol deviation
1070	Study vaccine dose not administered according to protocol: 
 
• Participants vaccinated with the correct vaccine but who regurgitated for one of the 2 doses and did not receive a vaccine replacement
 
• Participants for whom the second administered dose is not aligned with the first dose (e.g. HRV as second dose after a first dose with HRV PCV-free)
 
• Participant who did not receive the second dose
 
• Route of vaccination which is not oral
 

1080	Vaccine temperature deviation: Participants who have received a vaccine which had a temperature deviation qualified as inappropriate for use by Quality Assurance.
1090	Expired vaccine administered: Participants who received an expired vaccine

Code	Decode: Condition under which the code is used
2010	Protocol violation linked to the inclusion/exclusion criteria: Ineligible participants who was vaccinated (Refer to protocol Section 5 "Study population" for the exhaustive list of inclusion/exclusion criteria).
2020	Anti-RV IgA antibody concentration at pre-vaccination above or equal to 20 U/mL or initially unknown antibody status
2040	Administration of any medication from day 1 to the Visit 3 blood sample which is forbidden by the protocol (see Section 5.2 from the protocol)
2070	Concomitant infection not related to the vaccine which may influence immune response => who have concomitant infection up to Visit 3 blood sample, which may influence the immune system namely RV gastroenteritis, immunosuppressive or immunodeficient conditions identified before Visit 3.
2080	Non-compliance with vaccination schedule (including wrong and unknown dates): Participants who did not comply with the interval for dose 2 (Dose 2 should be between 28-48 days after Dose 1 i.e. Dose 2 date – Dose 1 date should be between 28-48 days).
2090	Non-compliance with the blood sampling schedule (including wrong and unknown dates) => Blood sample not collected within 28 days-48 days after the corresponding intervention
2100	Serological results not available post dose
2120	Obvious incoherence/abnormality or error in data

\* Forced randomization: In case of supplies shortage for the next assigned vaccine according to the randomization schedule at the clinical site, the randomization system will use the forced randomization procedure in order to continue to enrol and vaccinate participants. The system moves seamlessly to the next treatment/randomization number for which vaccine supplies are available. The site will not be aware of the forced randomization event.

\*Manual randomization: In case the randomization system is unavailable, the investigator has the option to perform randomization by selecting supplies available at the site according to a pre-defined rule. In case the randomization system is available, a vaccine different from the randomized treatment may have been administered at dose 1.

#### 6.1.4. Prior and Concomitant Medications

Summaries of co-administered vaccinations (i.e., vaccinations given on the day of each *Rotarix* dose) and intercurrent vaccinations (i.e., vaccinations other than *Rotarix* administered from birth up to Visit 3, excluding vaccination given on the day of *Rotarix* administration) will be provided for each group.

The percentages of participants who started taking at least 1 concomitant medication, by type (any, antipyretic), from Day 1 to Day 14 after study intervention administrations will be tabulated by group with the exact 95% CI.

The percentages of participants who started taking at least 1 concomitant medication, by type (any, antipyretic), within 1 month after each dose will also be tabulated by group with exact 95% CI.

#### 6.1.5. Study Intervention Compliance

The number of doses administered will be tabulated for each group for the ES. A dose is defined as a vaccination visit. Accordingly, a visit at which a replacement dose was given

following regurgitation will be counted as one dose. Note that participants without a replacement dose administered despite regurgitation will be summarized among the important protocol deviation summary.

### 6.1.6. Reactogenicity/Safety Compliance

The number and percentage of participants with symptom sheets returned with documented occurrence of at least one solicited symptom will be tabulated by group and by dose for the ES.

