9.4.1.2. Reactogenicity/Safety

Participants who missed reporting events (solicited/unsolicited AEs or concomitant medications) will be treated as participants without the events (solicited/unsolicited AEs or concomitant medications, respectively).

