#### 4.1.2. Reactogenicity

Participants without events (solicited/unsolicited AEs or concomitant medications) reported will be treated as participants without the events (solicited/unsolicited AEs or concomitant medications, respectively).

Refer to Section 6.2.4.2 for the intensity grading of solicited AEs.

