#### 4.5. Safety Analyses

The analyses will be descriptive and conducted on the ES.

The following calculations will be performed for each group:

- The percentage of doses and participants reporting at least 1 AE (solicited or unsolicited) during the 14-day (Day 1 to Day 14) solicited follow-up period will be computed, along with exact 95% CI. The same calculations will be done for AEs (solicited or unsolicited) rated as grade 3 in intensity and for AEs leading to a medically attended visit.
- The percentage of doses over the study and the percentage of participants (by dose and over the study) reporting each individual solicited systemic event will be computed, over the 14-day (Day 1 to Day 14) solicited follow-up period, following study intervention administration, along with exact 95% CI. The same calculations will be done for each individual solicited systemic event rated as grade 3 (grade 3 or grade 4 for fever) in intensity and events leading to a medically attended visit. Temperature above specific thresholds will also be summarized with threshold defined by half degree increment.

*Note: Intensity of fever will be assessed by considering the grading scales recommended by the Chinese authorities [NMPA 2019b].*

- The verbatim reports of unsolicited AEs will be reviewed by a physician and will be coded according to MedDRA. Every verbatim term will be matched with the appropriate Preferred Term. The percentage of participants with unsolicited AEs occurring within 31-day (Day 1 to Day 31) follow-up period after any dose with its exact 95% CI will be tabulated by Preferred Term. The same calculations will be done for each AE rated as grade 3 in intensity, for AEs leading to a medically attended visit and for AEs causally related to HRV as per the investigator assessment.
- The percentage of participants reporting the occurrence of SAEs (any, related, fatal, fatal related) from Dose 1 of the study intervention up to study end with its exact 95% CI will be tabulated by study group and by preferred term.
- The percentage of participants reporting the occurrence of SAEs (any, related, fatal, fatal related) within 31-day (Day 1 to Day 31) follow-up period after any dose with its exact 95% CI will be tabulated by study group and by preferred term.
- SAEs and drop outs due to AEs will be described in detail.

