### 6.2.4.2. Daily recording of solicited AEs

When a specific solicited AE is marked as having not occurred following a specific vaccination (i.e. SDTM CE.CEOCCUR=N for the specified post-vaccination period for the solicited AE in question), all daily measurements will be imputed as Grade 0.

When a specific solicited AE is marked as having occurred following a specific vaccination (i.e. SDTM CE.CEOCCUR=Y for the specified post-vaccination period for the solicited AE in question), any missing daily recordings will be given an imputed value which allows them to contribute to the 'Any' rows but not to specific grade rows of the solicited AE summary tables.

When the occurrence of a specific solicited AE is not present (i.e. SDTM CE.CEOCCUR is neither Y nor N for the specified post-vaccination period for the solicited AE in question) all missing daily recordings will be given an imputed value which allows them to contribute to the 'Any' rows but not to specific grade rows of the solicited AE summary tables.

The following table shows how solicited events are coded for intensity.

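### Read plainly, the reactogenicity compliance table in SAP 6.1.6 counts only symptomatic sheets, so the number of infants without diary data cannot be recovered

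*SAP*

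**What the plan says.** SAP 6.1.6 plans one compliance output, a count with its percentage, defined by this text: "symptom sheets returned with documented occurrence of at least one solicited symptom will be tabulated by group and by dose for the ES".

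Non-reporters are dealt with in three places.

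- Protocol 9.4.1.2: "Participants who missed reporting events (solicited/unsolicited AEs or concomitant medications) will be treated as participants without the events".
- SAP 4.1.2: "Participants without events (solicited/unsolicited AEs or concomitant medications) reported will be treated as participants without the events".
- SAP 6.2.4.2 has a separate rule for a blank status field. It opens "When the occurrence of a specific solicited AE is not present (i.e. SDTM CE.CEOCCUR is neither Y nor N", and provides that "all missing daily recordings will be given an imputed value which allows them to contribute to the" *Any* rows. The numerator table that follows SAP Table 6 defines *Any* differently: a missing day counts only where the event has been marked as present.

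On the safety outputs, SAP 4.5 states: "The analyses will be descriptive and conducted on the ES". It lists the percentage "reporting at least 1 AE (solicited or unsolicited) during the 14-day (Day 1 to Day 14) solicited follow-up period", and the percentage for each solicited event separately.

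No other section plans a count of returned or missing diary cards. SAP 6.1.1 covers enrolment, withdrawal and Per-Protocol exclusions, and SAP 6.1.5 covers doses administered. Protocol 10.3.6 does foresee unreturned cards, since it requires the site to pursue them.

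**The concern.** A compliance table should tell the reader how much of the solicited-event information was collected. For that, a sheet recording that nothing happened is as informative as one recording a symptom. The wording of SAP 6.1.6 admits only the second kind, so what it measures moves with reactogenicity as well as with diary return.

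Reactogenicity is a stated secondary objective, and readers will compare the two arms. The solicited percentages use the whole Exposed Set, so their meaning depends on how many infants had no diary data and how those infants were counted. The first is not shown by any planned output. The second is not settled, because the SAP's rules point in different directions. An arm with a low figure in the 6.1.6 table could have had fewer symptoms or fewer diaries, and the table could not say which.

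**Working it through.** The documents give no diary return rate and no solicited-event rate, so there is no planned figure to reproduce. The structure can be checked algebraically, and the size only by assumption.

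**Notation, per group and dose.** Let *r* be the share of Exposed Set participants with a returned sheet, and *q* the share of returned sheets with at least one solicited symptom. I take the denominator to be Exposed Set participants given that dose, and ignore partly completed sheets.

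- SAP 6.1.6 as worded: *r* × *q*.
- Rate of at least one solicited symptom, non-returners counted as event-free (SAP 4.1.2): *r* × *q*.
- The same rate if non-returners fall under the blank-status rule of SAP 6.2.4.2: *r* × *q* + (1 − *r*).
- Share without diary data: 1 − *r*, which cannot be obtained from *r* × *q*.

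**One displayed value, many return rates** (assumed *r* and *q*; 1000 per arm, as in SAP section 5):

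| *r* | *q* | 6.1.6 as worded | No diary | Event rate, missing = no | Event rate, missing = *Any* | Status-completed table |
|---|---|---|---|---|---|---|
| 1.00 | 0.450 | 45.0% | 0 | 45.0% | 45.0% | 100% |
| 0.95 | 0.474 | 45.0% | 50 | 45.0% | 50.0% | 95% |
| 0.90 | 0.500 | 45.0% | 100 | 45.0% | 55.0% | 90% |
| 0.75 | 0.600 | 45.0% | 250 | 45.0% | 70.0% | 75% |
| 0.60 | 0.750 | 45.0% | 400 | 45.0% | 85.0% | 60% |

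The rate among returned sheets alone is the *q* column, from 45.0% to 75.0%. The table as worded is the same in every row; a table of completed status would separate them.

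**Two arms.** Assume *q* = 0.45 in both arms, and return of 95% in one arm and 95%, 90% or 85% in the other.

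- Missing counted as no event: 0.45 × 0.95 = 42.75%, against 42.75%, 0.45 × 0.90 = 40.5%, or 0.45 × 0.85 = 38.25%. The second arm looks lower by 0, 2.25 or 4.5 points, and 6.1.6 shows the same figures.
- Missing counted in *Any*: 42.75 + 5 = 47.75%, against 47.75%, 40.5 + 10 = 50.5%, or 38.25 + 15 = 53.25%. The second arm now looks higher by 0, 2.75 or 5.5 points.

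The same missing diaries therefore shift the comparison in opposite directions, depending on which SAP rule is programmed.

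**The case against.** The strongest reply is that the wording was meant correctly. SAP 6.2.4.2 uses the word occurrence for the yes/no status field, and under a heading about compliance, a documented occurrence could mean that the status was filled in either way. That would give a true completeness rate. This stands as a plausible intent, but not as what the text says. SAP 6.2.8 and the numerator table after Table 6 use the same word for events that happened, so a programmer could reasonably build the wrong table.

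Three stronger readings are tempting, and the documents do not support them.

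- A reader might infer that 6.1.6 merely repeats a table planned under SAP 4.5. It does not. SAP 4.5 lists solicited and unsolicited AEs combined, and each solicited event separately; it lists no percentage for any solicited event alone.
- A reader might infer that missing diaries must lower the reported rates. That follows from SAP 4.1.2 and Protocol 9.4.1.2, but the blank-status rule in SAP 6.2.4.2 points the other way.
- A reader might infer that return will differ between arms. Nothing in the documents suggests it. Parents and clinical evaluators stay blinded (Protocol 6.3.4), and cards are checked at Visits 2 and 3 and pursued if missing (Protocol 10.3.6). These steps should limit missing diaries and any imbalance. They do not report what remains.

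It is also fair that the safety analyses are descriptive, with no margin or decision rule attached.

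**Conclusion.** The point holds as a defect of definition. On its plain wording, the only planned reactogenicity compliance summary does not measure compliance, and no other listed output shows how many infants lacked diary data. The identity *r* × *q* holds for any values, under the simplifications stated. The numerical effect, including the 0 to 400 infants behind a displayed 45.0% and the shifts between arms, rests wholly on assumed return and event rates, and on assuming that an unreturned diary reaches the dataset either as no report or as a blank status.

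The reach is limited to descriptive reactogenicity. The hierarchical non-inferiority tests are untouched. The change is worth making before the tables are programmed, because the conflict over blank records leaves the reader needing this count.

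**What to change.** Redefine SAP 6.1.6 as the number and percentage of administered doses, by group and by dose in the Exposed Set, for which the presence or absence of each solicited symptom is documented (CEOCCUR equal to Y or N). Keep the SAP 6.1.5 convention that a dose is a vaccination visit, so a replacement dose is not counted twice. Show the documented number beside each solicited-event percentage.

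At the same time, reconcile SAP 4.1.2 with the blank-status rule in SAP 6.2.4.2 and with the *Any* definition after Table 6, so that one rule governs infants with no symptom status.

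The cost is a small change to SAP wording and table programming. The status field is already part of the planned dataset. The definition should rest on that field rather than on physical return of the card: the Schedule of Activities marks card return with a different symbol from transcription, which I read as meaning that return itself is not recorded in the eCRF.
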